## 2.2. Primary and Secondary Measures and Endpoints

### 2.2.1. Primary Efficacy Measure and Endpoint

The primary efficacy endpoint for this study is the change from baseline to week 4 in the weekly average of the daily average NRS scores. The daily average NRS score is the average of the 2 NRS scores (recorded in the morning and evening) of average pain, defined as the patient-reported average pain intensity over the prior 12 hours.

### 2.2.2. Secondary Efficacy Measures and Endpoints

The secondary efficacy endpoints for this study are as follows:

- Change from baseline to weeks 1, 2, 3 and 4 in the weekly average of the average pain score recorded in the evening
- Change from baseline to weeks 1, 2, 3 and 4 in the weekly average of the average pain score recorded in the morning
- Change from baseline to weeks 1, 2, 3 and 4 in the weekly average of the worst pain score recorded in the evening (worst pain is defined as the patient-reported worst pain intensity over the prior 24 hours)
- Percentage of patients with  $\geq 30\%$  improvement from baseline in the weekly average of the daily average NRS scores at week 4
- Percentage of patients with  $\geq 50\%$  improvement from baseline in the weekly average of the daily average NRS scores at week 4
- Change from baseline (randomization visit) to weeks 2 and week 4 in the NPSI score
- Change from baseline (randomization visit) to week 4 in the NePIQoL score
- Patients' global assessment of treatment, as measured by PGIC scores, at weeks 2 and 4
- Change from baseline (randomization visit) in DSIS scores at weeks 2 and 4
- First time to reach  $\geq 30\%$  sustained improvement from baseline in the weekly average of the daily average NRS scores
- Change from baseline (randomization visit) to weeks 2 and 4 in maximal intensity of patients' brush-evoked allodynia, as measured on the 11-point NRS
- Change from baseline (randomization visit) to weeks 2 and 4 in maximal intensity of patients' punctate-evoked hyperalgesia, as measured on the 11-point NRS using a Medipin

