3.3.2. Secondary Efficacy Measures and Endpoints

The secondary efficacy measures and endpoints for this study are as follows:

- change from baseline to week 4 in the weekly average of the average pain score recorded in the evening
- change from baseline to week 4 in the weekly average of the average pain score recorded in the morning
- change from baseline to week 4 in the weekly average of the worst pain score recorded in the evening (worst pain is defined as the patient-reported worst pain intensity over the prior 24 hours)
- percentage of patients with $\geq 30\%$ improvement from baseline in the weekly average of the daily average NRS scores at week 4
- percentage of patients with $\geq 50\%$ improvement from baseline in the weekly average of the daily average NRS scores at week 4
- change from baseline (randomization visit) to weeks 2 and 4 in the NPSI score
- change from baseline (randomization visit) to week 4 in the NePIQoL score
- patients' global assessment of treatment, as measured by PGIC scores, at weeks 2 and 4
- change from baseline (randomization visit) in DSIS scores at weeks 2 and 4
- time to reach $\geq 30\%$ improvement from baseline (randomization visit) in the weekly average of the daily average NRS scores
- change from baseline to weeks 2 and 4 in maximal intensity of patients' brush-evoked allodynia, as measured on the 11-point NRS

- change from baseline to weeks 2 and 4 in maximal intensity of patients' punctate-evoked hyperalgesia, as measured on the 11-point NRS using a Medipin

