9.6.1.3. Secondary Efficacy Analysis

The continuous secondary efficacy variables will be analyzed in a similar way as the primary efficacy variable.

The percentages of patients with $\geq 30\%$ and $\geq 50\%$ improvement from baseline in weekly average NRS scores at week 4 will be summarized using descriptive statistics. The time to reach $\geq 30\%$ improvement in weekly average NRS scores from baseline will also be summarized using descriptive statistics.

PGIC scores will be analyzed using a MMRM model with week, treatment, and treatment by week interaction as fixed factors and patient as a random factor. The unstructured covariance matrix for repeated observations within patients will be used.

NePIQoL score will be analyzed using an analysis of covariance (ANCOVA) model with effects due to baseline and treatment, imputing missing data via last observation carried forward (LOCF).

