### 1.2. Secondary Objectives

The secondary objectives of the study are as follows:

- To evaluate the efficacy of topical TV-45070 (4% and 8% ointment) compared with placebo by examining the following:
  - Change from baseline to week 4 in the weekly average of the average pain score recorded in the evening
  - Change from baseline to week 4 in the weekly average of the average pain score recorded in the morning
  - Change from baseline to week 4 in the weekly average of the worst pain score recorded in the evening (worst pain is defined as the patient-reported worst pain intensity over the prior 24 hours)
  - Percentage of patients with  $\geq 30\%$  improvement from baseline in the weekly average of the daily average NRS scores at week 4
  - Percentage of patients with  $\geq 50\%$  improvement from baseline in the weekly average of the daily average NRS scores at week 4
  - Change from baseline (randomization visit) to weeks 2 and 4 in the Neuropathic Pain Symptom Inventory (NPSI) score
  - Change from baseline (randomization visit) to week 4 in the Neuropathic Pain Impact on Quality of Life (NePIQoL)
  - Patient's global assessment of treatment as measured by the Patient Global Impression of Change (PGIC) scores at weeks 2 and 4
  - Change from baseline (randomization visit) in the Daily Sleep Interference Scale (DSIS) at weeks 2 and 4
  - Time to reach  $\geq 30\%$  improvement from baseline in the weekly average of the daily average NRS scores
  - Change from baseline (randomization visit) in maximal intensity of patients' brush-evoked allodynia, as measured on 11-point NRS at weeks 2 and 4

- Change from baseline (randomization visit) in maximal intensity of patients' punctate-evoked hyperalgesia, as measured on 11-point NRS using a Medipin® (US Neurologicals, LLC / Medipin Ltd), at weeks 2 and 4
- To characterize the pharmacokinetics of TV-45070 in terms of the following. This will be conducted in another analysis plan.
  - Establishing the dose-exposure relationship of topical TV-45070 (4% and 8% w/w ointment under multiple-dose conditions in patients with PHN)
  - Estimating the apparent clearance (CL/F) and volume of distribution (V/F) of TV-45070 by incorporating the concentration data of this study into an enriched TV-45070 pharmacokinetics database and performing population pharmacokinetic modeling

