- NePQoL is a questionnaire that contains 41 items to evaluate quality of life in patients with neuropathic pain. Each question has responses ranging from strongly agree or always to strongly disagree or never. Questions are scored on a 5-point scale from 1 to 5, where higher scores represent greater pain-related interference in the quality of life (four items will have scores inverted so that higher scores reflect greater pain. “I involve myself with people I am close to as much as I used to despite the pain”, “I can distract myself from the pain”, “I can cope with the pain”, and “I still enjoy my hobbies/leisure activities despite the pain.”). The total score is calculated as the sum of the scores for the individual questions (Poole and Nurmikko 2009). If scores for up to 4 questions are missing then the total score will be computed as 41 times sum of non-missing scores divided by the number of non-missing questions. If responses for more than 4 questions are missing then the total score will be considered missing.
- PGIC is a standardized self-report tool that measures the change in a patient's overall status rating since the start of treatment (Hurst and Bolton 2004) on 7-point scale. The 7-point scale is defined as: 1=very much improved, 2=much improved, 3=minimally improved, 4=no change, 5=minimally worse, 6=much worse, 7=very much worse.
- DSIS is an 11-point scale that asks the patient to “select the number that best describes how much your pain has interfered with your sleep during the past 24 hours.” Response options range from 0 (Did not interfere with sleep) to 10 (Completely interfered with sleep/unable to sleep due to pain).
- First time to reach  $\geq 30\%$  sustained improvement from baseline in the weekly average of the daily average NRS scores will be computed in days from the date of first dose, where the date of first dose is day 1. Those who do not achieve  $\geq 30\%$  sustained improvement from baseline will be censored at date of last dose of study medication. Sustained improvement is defined as an improvement of  $\geq 30\%$  that is maintained until the end of the treatment period.
- Maximal intensity of patients' brush-evoked allodynia, as measured on the 11-point NRS.
- Maximal intensity of patients' punctate-evoked hyperalgesia, as measured on the 11-point NRS using a Medipin.

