## **10. CHANGES TO PROTOCOL SPECIFIED ANALYSES**

Protocol Section 9.5.2, Demographics and Baseline Characteristics, states that treatment groups will be compared for all categorical variables using a Pearson chi-square (or Fisher's exact test if cell sizes are too small). No comparisons will be done for demographic variables.

Protocol Section 9.6.1.1, Primary Efficacy Analysis, states that the MMRM model will analyze change from baseline in the weekly average of the daily average NRS scores at weeks 2 and 4 as the dependent variable. The change from baseline in the weekly average of the daily average NRS scores at weeks 1, 2, 3, and 4 will be used. Weeks 1 and 3 will also be included in the model.

Protocol Section 9.6.1.3, Secondary Efficacy Analysis, states that the time to reach  $\geq 30\%$  improvement in weekly average NRS scores from baseline will be summarized using descriptive statistics. This analysis will be reporting using Kaplan-Meier.

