15.2.10.1	First Time to Reach 30% or More Sustained Improvement in Weekly Average of the Daily Average NRS Pain Scores	Full Analysis Set
15.2.11.1	Summary of Change from Baseline in Maximal Intensity of Brush-Evoked Allodynia as Measured on 11-point NRS	Full Analysis Set
15.2.12.1	Summary of Change from Baseline in Maximal Intensity of Punctate-Evoked Hyperalgesia as Measured on 11-point NRS	Full Analysis Set
15.2.13.1		Full Analysis Set
15.2.13.2		Per Protocol Population
15.2.13.3		Full Analysis Set
15.2.13.4		Full Analysis Set
15.2.13.5		Full Analysis Set
15.2.13.6		Full Analysis Set
15.2.13.7		Per Protocol Population
15.2.13.8		Full Analysis Set
15.2.13.9		Full Analysis Set
15.2.13.10		Full Analysis Set
15.2.13.11		Full Analysis Set
15.2.13.12		Full Analysis Set
15.2.13.13		Full Analysis Set
15.2.13.14		Full Analysis Set

Summary number	Title	Population
15.2.14	[REDACTED]	Full Analysis Set
15.2.15.1	[REDACTED]	Full Analysis Set
15.2.15.2	[REDACTED]	Full Analysis Set
15.2.15.3	[REDACTED]	Full Analysis Set
15.2.15.4	[REDACTED]	Full Analysis Set
15.2.16	Association of CYP3A4 and CYP2C19 with Response Variables	Full Analysis Set
15.3.1.1	Study Drug Exposure by Treatment Group	Safety Analysis Set
15.3.1.2	Study Drug Compliance by Treatment Group	Safety Analysis Set
15.3.1.3	Pharmacokinetic Plasma Concentrations	Safety Analysis Set
15.3.2	Treatment Emergent Adverse Events by System Organ Class, Preferred Term, and Treatment Group	Safety Analysis Set
15.3.3	Treatment Emergent Adverse Events by System Organ Class, Preferred Term, Severity, and Treatment Group	Safety Analysis Set
15.3.4	Treatment-Related Adverse Events by System Organ Class, Preferred Term, and Treatment Group	Safety Analysis Set
15.3.5	Treatment-Related Adverse Events by System Organ Class, Preferred Term, Severity, and Treatment Group	Safety Analysis Set
15.3.6	Treatment Emergent Adverse Events by System Organ Class, Preferred Term, Causality, and Treatment Group	Safety Analysis Set
15.3.7	Treatment Emergent Serious Adverse Events by System Organ Class, Preferred Term, and Treatment Group	Safety Analysis Set
15.3.8	Treatment Emergent Adverse Events Causing Discontinuation From the Study by System Organ Class, Preferred Term, and Treatment Group	Safety Analysis Set
15.3.9	Treatment Emergent Non-Serious Adverse Events by System Organ Class, Preferred Term, and Treatment Group	Safety Analysis Set

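### The SAP analyses only time to a sustained 30% improvement, so no readable output estimates the time to first 30% improvement that the protocol and SAP 1.2 both list

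*SAP*

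**What the plan says.** **Protocol.** Sections 2.2.2 and 3.3.2 list time to reach at least 30% "improvement from baseline (randomization visit) in the weekly average of the daily average NRS scores" (the 3.3.2 wording). Section 9.6.1.3 plans that time to at least 30% "improvement in weekly average NRS scores from baseline will also be summarized using descriptive statistics". None of these requires the improvement to last.

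**SAP objectives.** Section 1.2 keeps the protocol's form: time to reach at least 30% "improvement from baseline in the weekly average of the daily average NRS scores".

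**SAP endpoint, definition and analysis.** Section 2.2.2 turns this into the first time to at least 30% "sustained improvement from baseline in the weekly average of the daily average NRS scores". Section 6.3.1 defines sustained as an improvement "that is maintained until the end of the treatment period" and states that patients who do not achieve at least 30% "sustained improvement from baseline will be censored at date of last dose of study medication". Section 6.3.2 applies Kaplan-Meier to this version. Table 15.2.10.1 is titled "First Time to Reach 30% or More Sustained Improvement in Weekly Average of the Daily Average NRS Pain Scores", and Graph 17.6 plots the same quantity.

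**SAP section 10.** The entry for this endpoint names it without the sustained condition and records only the change of method: "This analysis will be reporting using Kaplan-Meier".

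**The concern.** The two definitions answer different questions. The protocol's version asks how soon a patient first has meaningful relief. The SAP's version asks when relief began among patients who still had it at the end of treatment, and it treats everyone else as having no event. If the SAP is followed as written, a listed secondary objective ends without an estimate.

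The change is also hard to see. A reader of section 10 would conclude that the endpoint is intact and only the summary method has moved. The SAP thus disagrees with itself: sections 1.2 and 10 use one definition, and sections 2.2.2, 6.3.1, 6.3.2, 12.1 and 12.3 use the other.

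**Working it through.** The plan gives no figure for this endpoint, so there is none to reproduce. The check is logical first and illustrative second.

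**1. What the definitions do to one patient.** Take a hypothetical baseline of 6.0, so the 30% threshold is 0.7 × 6.0 = 4.2. Suppose the weekly averages are 4.0, 4.1, 4.8 and 5.0. The improvements are 2.0/6.0 = 33%, 1.9/6.0 = 32%, 1.2/6.0 = 20% and 1.0/6.0 = 17%. Under the protocol's wording the patient reaches 30% in week 1. Under SAP 6.3.1 the patient has no event and is censored at last dose.

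**2. Where the sustained curve ends.** SAP 6.2.1 gives four weekly averages, so a response lasting to the end of treatment must be present at week 4. Conversely, any patient with at least 30% improvement at week 4 has a sustained response starting at week 4 or earlier. With complete data the final sustained proportion therefore equals the week 4 responder rate. The curve adds timing among those patients but no new total.

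**3. How much the definitions can differ.** All inputs here are assumptions except the SD of 2.35, which is borrowed from SAP 2.3.
- Baseline has mean 6.2 and SD 1.2. Scores are limited to 0–10. There is no dropout.
- Weekly changes are multivariate normal with AR(1) correlation 0.8. The SDs at weeks 1 to 4 are 0.6, 0.8, 0.92 and 1.0 times 2.35.
- Placebo mean changes are −0.6, −1.0, −1.3 and −1.5.

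| Arm (mean change, weeks 1–4) | Ever ≥30% by week 4 | Sustained ≥30% | Gap from placebo, ever | Gap from placebo, sustained |
|---|---|---|---|---|
| Placebo | 57% | 44% | – | – |
| Early, waning (−1.8, −2.0, −1.9, −1.8) | 72% | 49% | 72 − 57 = 15 | 49 − 44 = 5 |
| Builds to 1.0 (−1.0, −1.75, −2.25, −2.5) | 73% | 61% | 73 − 57 = 16 | 61 − 44 = 17 |
| Early, persisting (−1.6, −2.0, −2.3, −2.5) | 76% | 61% | 76 − 57 = 19 | 61 − 44 = 17 |

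At week 1 the gaps are about 29 (first response) versus 15 points (sustained) in the waning case, and about 9 versus 9 when the effect builds. With correlation from 0.7 to 0.9, the waning-case gaps at week 4 stay at 14–15 versus about 5.

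**4. A second set of assumptions.** Baseline has mean 6.3, SD 1.2, limited to 4–9. The SD is 2.35 at every week. The week 4 change is −1.5 (placebo) or −2.5 (active), with 40, 70, 90 and 100% of it reached by weeks 1 to 4. Correlation is 0.6 to 0.9. On placebo 54–69% ever reach 30%, against about 44% sustained. On active the figures are 68–82% against 60%. The share of ever-responders who end with no event runs from 1 − 60.1/68.2 = 12% (active, correlation 0.9) to 1 − 43.5/69.1 = 37% (placebo, correlation 0.6).

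**The case against.** **Early effect is not hidden.** SAP 6.2.2 reports LS mean differences with confidence intervals at weeks 1, 2, 3 and 4, and Graph 17.1.1 plots weekly means by arm. In the waning scenario the mean differences are −1.2, −1.0, −0.6 and −0.3, a pattern those outputs would show. This stands. A reader might infer that the trial cannot say anything about onset; the documents do not support that. What is missing is the patient-level time to first response, which group means do not give.

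**The contrast need not shrink.** This also stands. A reader might infer that the sustained version generally masks a treatment effect. It does so markedly only if the effect wanes, and nothing in the documents predicts waning.

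**Redactions.** SAP 6.4 and several exploratory table and graph titles cannot be read, so it cannot be said that the protocol's endpoint is analysed nowhere. The secondary-endpoint sections, where it belongs, are readable and contain only the sustained version.

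**The SAP may change the endpoint.** The SAP preface says that the SAP prevails and that the clinical study report will explain discrepancies. Protocol 9.13 allows deviations to be described in the plan or that report. A sustained-response criterion is a legitimate, stricter choice, and it is openly defined. So the fault is not that a change was made. Precedence over the protocol, however, neither resolves a conflict inside the SAP nor supplies the missing estimate.

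**Conclusion.** The point holds in a limited form. A secondary endpoint was redefined, section 10 presents this as a change of method only, and no readable output estimates time to first 30% improvement. That rests on the text alone.

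The size rests on assumptions. In the two illustrations the week 4 treatment gap moves from about 15 to 5 points under a waning effect and hardly at all (16 to 17) under one that builds, while 12–37% of patients who ever reach 30% are recorded without an event in the second set. Both illustrations ignore dropout, which the plan puts at about 20%.

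This is a minor point. The endpoint is secondary in a Phase 2 study, the protocol planned only to describe it, and there is no multiplicity scheme for it to disturb. The primary analysis and sample size do not change.

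**What to change.** Before unblinding:

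1. Add a Kaplan-Meier table and plot of time to the first week with at least 30% improvement, as the protocol-defined secondary analysis.
2. Keep the sustained version beside it as an additional endpoint.
3. Declare the addition and its definition in SAP section 10, and align SAP 1.2 and 2.2.2.
4. While editing 6.3.1, state which study day counts as the event when a weekly average first qualifies, and what the end of the treatment period means for a patient who withdraws early. The section reports time in days but settles neither.

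The cost is one table, one plot and a few lines of text, using weekly averages that are already computed. Declaring the redefinition in section 10 and aligning 1.2 to it would be the least that removes the contradiction, but it would still leave the protocol's objective without an estimate.

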### 2.2.3. Exploratory Efficacy Measures and Endpoints

- [REDACTED]

#### **2.2.4. Safety Measures and Endpoints**

The safety of TV-45070 (4% and 8% ointment) will be assessed throughout the study by evaluating AEs, clinical safety laboratory test results, vital signs measurements, ECG findings, physical examination results, dermal irritation findings and concomitant medication usage. Skin rashes or skin irritation in the area of ointment application will be evaluated using a dermal irritation scale (modified Draize scale) at day 1 (at 1 hour after application of study drug), week 2, week 4, and week 8 for follow-up.

#### **2.2.5. Tolerability Measures and Endpoints**

The tolerability of TV-45070 (4% and 8% ointment) will be assessed during the study by using safety endpoints that also represent patients' experience of treatment, such as skin rashes and skin irritation.

#### **2.2.6. Pharmacokinetic Measures and Endpoints**

Two blood samples will be collected from each patient following 2 weeks of treatment with either 4% or 8% w/w TV-45070 ointment or matching placebo ointment, to quantitate the concentration of TV-45070 in plasma. Plasma samples will be analyzed for TV-45070. Population pharmacokinetic parameters, such as CL/F and V/F will be estimated when the sparse data from this study are combined with enriched pharmacokinetic data from other studies with topical TV-45070. A summary and listing of these results may be included in this study. These results will also be reported separately from the main study results.

### **2.2.7. Pharmacodynamic Measures and Endpoints**

Pharmacodynamic endpoints assessed during the study are the following secondary efficacy endpoints: change from baseline in maximal intensity of patients' brush-evoked allodynia and maximal intensity of punctate-evoked hyperalgesia.

### **2.2.8. Pharmacogenomic Analyses**

[REDACTED] A pharmacogenomic blood sample may be used to assess the polymorphisms for CYP3A4 and CYP2C19 genes. Depending on the distribution of the allelic variations, these variations may be incorporated as covariates in the current or future population pharmacokinetic analyses. Exploratory analyses may be reported separately from the main study results.

## **2.3. Sample Size and Power Considerations**

In prior studies of gabapentin or pregabalin treatment of PHN, the difference in mean pain scores between active- and placebo-treated groups ranged from 1.0 to 1.3. For this study, a conservative estimate of 1.0 will be used. Assuming a standard deviation of 2.35, a sample size of 88 per arm (a total of 264 patients) would be needed to provide 80% power with a 2-sided test at 5% significance level to detect a 1.0-point difference. Assuming an approximately 20% dropout rate, 110 patients per arm (a total of 330 patients) will be randomly assigned to each treatment group.

## **2.4. Randomization and Blinding**

This is a randomized, double-blind, placebo-controlled study. All tubes of study drug will be identical, and the ointments will be indistinguishable. Patients, investigators, and all clinical study center staff will remain blinded to treatment assignment during the study. Eligible patients will be randomly assigned via interactive-response technology (IRT) in a 1:1:1 ratio to 4% w/w TV-45070 ointment, 8% w/w TV-45070 ointment, or placebo ointment. Randomization will be stratified by the R1150W underlying genotype in the SCN9A gene: homozygous minor allele (positive, AA), heterozygous (positive, AG), and homozygous common allele (negative, GG).

In addition, the Sponsor's clinical personnel involved in the study will be blinded to the study drug identity until the database is locked for analysis and the treatment assignment revealed. A statistician not assigned to the study will be responsible for the randomization code, and the final randomization code will be maintained by the service provider.

Patients will be randomly assigned to treatment through a qualified randomization service provider (eg, IRT). This system will be used to ensure a balance across treatment groups; no effort will be made to maintain a balance among treatment groups within a study center.

The clinical study center will receive study drug kits, and kits will be assigned to individual patients by the IRT system based on the patients' randomization assignments. The IRT system will record the kit numbers for all patients. Designated study center staff, who will remain blinded to the treatment assignments, will dispense the kits to patients based on the kit numbers

assigned to patients by the IRT system. In case of emergency, the investigator and designated study center staff can call the IRT system to unblind the treatment for a specific patient.

